3.3. Justification for Study Design and Selection of Population

It is very important to recognize the significant difficulty of asking patients with CH to continue in a double-blind, placebo-controlled study beyond 3 months. Hence, in the current study, all patients will receive fremanezumab so that all patients have the opportunity to receive potential benefit from therapeutic doses including the loading dose of 675 mg sc. The dosing regimens planned for this study are consistent with dosing regimens in the pivotal studies. Refer to Section 5.3 for additional details regarding the rationale for the doses and dose regimens.

This study is double-blind to ensure impartiality in evaluating the long-term safety and efficacy of different dose regimens of fremanezumab and to avoid unblinding the pivotal studies before they are completed. The blind will be maintained according to standard blinding procedures (see Section 5.9.2) and through the use of dummy injections to ensure that number of injections is the same at each visit for patients with ECH and patients with CCH (see Section 5.1.1.1). After 15 June 2018, only patients who participated in the ECH study (Study TV48125-CNS-30056) will be enrolled for active treatment.

The study population will be composed of male and female patients, aged 18 to 70 years, inclusive, with a history of CCH or ECH (as defined by International Classification of Headache Disorders-third edition beta [ICHD-3 beta] criteria [[Headache Classification Committee of the IHS 2013](#)]) for at least 12 months prior to screening. Concomitant medications that are commonly prescribed for the preventive treatment of CH (listed in [Appendix H](#)) are prohibited throughout this study so that effects of the test IMP can be distinguished from effects of these concomitant preventive medications. Thus, patients who were taking concomitant preventive

medications during the pivotal studies will be required to taper off these medications during the first month of treatment in this study.

CH is an intensely painful primary headache disorder, and there is a significant unmet medical need for preventive treatments for CH.

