4.1. Patient Inclusion Criteria

Patients may be included in the treatment portion of the study only if they meet all of the following criteria:

- a. The patient is a male or female and 18 to 70 years of age, inclusive, at the start of the pivotal study.
- b. The patient signs and dates the informed consent document.
- c. The patient completes either the Phase 3 pivotal study for ECH (Study TV48125-CNS-30056) or the Phase 3 pivotal study for CCH (Study TV48125-CNS-30057) without important protocol deviations related to patient safety and patient compliance and at least 75% diary data completion during the pivotal study. Prior to 15 June 2018, patients from the ECH study and the CCH study were enrolled. After 15 June 2018, only patients who participated in the ECH study (Study TV48125-CNS-30056) will be enrolled for active treatment.
 - In addition, patients who do not complete the pivotal efficacy studies, and patients who complete the pivotal efficacy studies but do not wish to continue treatment during this long-term safety study, will be offered to enroll in this study for the purpose of evaluating ADAs and safety (adverse events and concomitant medications) approximately 7.5 months after administration of the last dose of the IMP.
- d. Women may be included only if they have a negative beta-human chorionic gonadotropin (β -HCG) test at visit 1, are sterile or postmenopausal, and are not lactating (not applicable for patients participating in safety follow-up only). Definitions of sterile and postmenopausal are given in [Appendix E](#).
- e. Women of childbearing potential (WOCBP) whose male partners are potentially fertile (ie, no vasectomy) must use highly effective birth control methods (see [Appendix E](#)) for the duration of the study and for 7.5 months after discontinuation of IMP.

Men must be sterile or, if they are potentially fertile/reproductively competent (not surgically [eg, vasectomy] or congenitally sterile), and their female partners are of childbearing potential, must agree to use, together with their female partners, acceptable birth control methods for the duration of the study and for 7.5 months after administration of IMP.

Definitions of women of non-childbearing potential, sterile and postmenopausal women; male contraception; and highly effective and acceptable birth control methods, including examples, are given in [Appendix E](#).

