- f. The patient must be willing to stop concomitant medications used in clinical practice for the prevention of CH (ie, verapamil, topiramate, valproate, lithium, or methysergide) for the duration of this study. Patients must begin tapering these preventive medications as soon as they begin this study. The period of time needed to taper off these medications will be based on the investigator's medical judgment but should not exceed 1 month from the beginning of participation in this study ([Appendix H](#)) (not applicable for patients participating in safety follow-up only).
- g. The patient is in good health in the opinion of the investigator, as determined by a medical and psychiatric history; medical examination; 12-lead ECG; and serum chemistry, hematology, coagulation, and urinalysis (not applicable for patients participating in safety follow-up only).
- h. The patient must be willing and able to comply with study restrictions to remain at the clinic for the required duration during the study period and to return to the clinic for the follow-up evaluations, as specified in this protocol.

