4.3. Withdrawal Criteria and Procedures for the Patient

Each patient is free to withdraw from this study at any time, without prejudice to their continued care. Patients must be withdrawn from this study if any of the following events occur:

1. Patient withdraws consent or requests discontinuation from this study for any reason.
2. Patient develops an illness that would interfere with his/her continued participation.

3. Patient is noncompliant with the study procedures and assessments or administration of IMPs (including noncompliance with wearable sensor substudy, if applicable) in the opinion of the investigator.
4. Patient takes prohibited concomitant medications as defined in this protocol.
5. A female patient has a confirmation of pregnancy during the study from a positive pregnancy test result.
6. The sponsor requests withdrawal of the patient.
7. Patient experiences an adverse event or other medical condition which indicates to the investigator that continued participation is not in the best interest of the patient.
8. The investigator and/or sponsor may withdraw an individual patient from the study at any time for any reason (eg, lack of efficacy, protocol deviation as defined in Section 10, noncompliance, or adverse event). In addition, patients with positive eC-SSRS findings or abnormal hepatic laboratory values (eg, ALT, AST, ALP, GGT, bilirubin [total, direct, or indirect], or INR) may meet criteria for discontinuation from the IMP as summarized in [Appendix J](#).

In the event that a patient was incorrectly enrolled and has already started taking the study drug, a risk/benefit evaluation should take place between the investigator and sponsor, and a strong clinical justification must be provided if the patient is not withdrawn from study drug.

Patients should be treated with standard of care after withdrawal from or termination of the study as appropriate.

Investigators should attempt to obtain information on patients in the case of withdrawal or discontinuation. Results of any evaluations and observations, together with a narrative describing the reason(s) for withdrawal, must be recorded in the source documents. The case report form (CRF) must document the primary reason for withdrawal or discontinuation.

See [Appendix F](#) for information regarding how the study will define and address lost to follow-up patients to help limit the amount and impact of missing data.

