APPENDIX C. QUALITY CONTROL AND QUALITY ASSURANCE

Protocol Amendments and Protocol Deviations

Protocol Amendments

No changes from the final approved (signed) protocol will be initiated without the prior written approval or favorable opinion of a written amendment by the Independent Ethics Committee/Institutional Review Board (IEC/IRB) and national and local competent authorities, as applicable, except when necessary to address immediate safety concerns to the patients or when the change involves only nonsubstantial logistics or administration. The principal investigator at each investigational center, the coordinating investigator (if applicable), and the sponsor will sign the protocol amendment.

Protocol Deviations

Any deviation from the protocol that affects, to a significant degree, (a) the safety, physical, or mental integrity of the patients in the study and/or (b) the scientific value of the study will be considered an important protocol deviation. Important protocol deviations may include non-adherence on the part of the patient, the investigator, or the sponsor to protocol-specific inclusion and exclusion criteria, primary objective variable criteria, or Good Clinical Practice (GCP) guidelines; noncompliance to investigational medicinal product administration; and use of prohibited medications. All protocol deviations will be reported to the responsible IEC/IRB, as required.

When an important protocol deviation is reported, the sponsor will determine whether to discontinue the patient from the study or permit the patient to continue in the study, with documented approval from the medical expert. The decision will be based on ensuring the safety of the patient and preserving the integrity of the study. A noncompliant patient may continue taking the study treatment only if this does not jeopardize the patient's safety. The sponsor will assess each protocol deviation and decide whether any of these noncompliances should be reported to the Regulatory Authority as a serious breach of Good Clinical Practice (GCP) and the protocol.

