APPENDIX H. PREVENTIVE CLUSTER HEADACHE MEDICATIONS AND DISALLOWED MEDICATIONS

Disallowed Medications Commonly Prescribed for Cluster Headache

The following medications will be considered as being used for the prevention of cluster headache attacks regardless of the initial indication:

- verapamil
- lithium
- methysergide
- valproate
- topiramate

Patients must start tapering these preventive medications as soon as they begin this study. The period of time needed to taper off these medications will be based on the investigator's medical judgment but should not exceed 1 month from the beginning of participation in this study.

Disallowed Concomitant Medications

Systemic steroids are not allowed during the double-blind treatment period of this long-term extension study.

Note that the only allowed steroids are intra-articular injection or ocular, ear drops, intranasal, inhaled, and creams for topical use.

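### The ban on preventive drugs has no stated end and its breach means withdrawal, yet the protocol calls for standard of care once dosing is over (minor)

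*Protocol*

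**What the plan says.** On the ban and its consequence:

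- Protocol 4.1 f, and its copy in the Synopsis, names the drugs and the period: "ie, verapamil, topiramate, valproate, lithium, or methysergide) for the duration of this study". The only exception written there is for patients in safety follow-up alone.
- Section 3.3 says that preventives "are prohibited throughout this study so that effects of the test IMP can be distinguished" from those of the preventives.
- Section 5.5, to which 7.10 sends the reader for prohibited medications, gives patients 1 month to be off the five drugs. It says nothing about when they may resume.
- Appendix H introduces its list with "The following medications will be considered as being used for the prevention of cluster headache attacks regardless of the initial indication" and states no period. The same appendix does confine the ban on systemic steroids to the double-blind treatment period.
- Section 4.3 opens with "Patients must be withdrawn from this study if any of the following events occur", and item 4 reads "Patient takes prohibited concomitant medications as defined in this protocol". No period is attached.

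On care after dosing:

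- Section 3.1 says that patients who are no longer dosed and are waiting for antidrug-antibody (ADA) evaluation should receive standard of care.
- Table 4 footnote k says the same for patients past the EOT/early withdrawal visit.
- Appendix B, on procedures after treatment, says patients may receive it after visit 11.

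**The concern.** The two sets of instructions cover the same patients over the same weeks. Section 1.1.2 presents verapamil as the usual first choice for prevention and also lists topiramate, valproic acid and lithium. Standard of care for cluster headache therefore includes drugs on the banned list. An investigator who follows 3.1 or footnote k and prescribes verapamil after EOT has, on the wording of 4.3, a patient who must be withdrawn.

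Two things are at stake. One is patient care: a site reading 4.3 strictly may hold back a preventive in order to keep the patient in the study. The other is the completeness of late safety and ADA follow-up, if withdrawn patients come back less reliably. Patients with chronic cluster headache (CCH) who were dosed in this study are the clearest case. They have been asked to stop the study drug and encouraged to stay in follow-up (1.1.3), and 5.3.1 describes their pain as continuous.

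**Working it through.** No planned figure is at issue, so the check is a comparison of text plus the length of the window.

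**1. Does *study* include the weeks after EOT?** Yes, in most places. Section 3.1 describes a 68-week study and sets its end at the last patient's follow-up visit. The Synopsis gives participation as about 68 weeks. Section 5.5 records medication to the end of the study including follow-up, and 7.1.2 runs the adverse-event period through the follow-up visit. Two places point the other way. Appendix B treats a patient compliant from visit 1 through visit 11 as having completed the study, and 4.1 e separates the study's duration from the 7.5 months after the study drug.

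**2. Does any section end the ban?**

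- 4.1 f and Synopsis: duration of the study.
- 3.3: throughout the study.
- 5.5: a date to be off the drugs, none to resume.
- Appendix H: no period for preventives, although one is given for steroids.
- 4.3 item 4: no period.

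None of them does.

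**3. Who is exempt?** Sections 4.1 f and 5.5 exempt patients in safety follow-up only. Table 5 describes that group as rolling over from the pivotal studies for ADA and safety evaluation only. A patient dosed in this study entered under 4.1 f and does not literally belong to it.

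**4. Do banned drugs count as standard of care?** Section 1.1.2 names verapamil, topiramate, valproate (as valproic acid) and lithium: 4 of the 5. Methysergide is not named there.

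**5. How long is the overlap for a full-course patient?**

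- From EOT (week 40) to visit 12 (week 68): 68 − 40 = 28 weeks, and 28/68 = 41% of planned participation.
- From the last dose (week 36): 68 − 36 = 32 weeks.

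**6. What is scheduled in the overlap?** One visit, visit 12. ADA samples in Table 4 fall at weeks 12, 24, 36, 40 and 68, so 1 of 5 lies after EOT.

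**7. Is visit 12 lost on withdrawal?** Not by rule. Appendix B still asks patients who stop treatment and withdraw to return about 7.5 months after the last dose, if at all possible.

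**The case against.** The strongest reply is that the conflict appears only if general text is read at its most literal. The standard-of-care statements deal specifically with the undosed period, and specific text normally governs. The lead-in to 4.1, "Patients may be included in the treatment portion of the study only if they meet all of the following criteria", ties criterion f to treatment, and f is itself an entry criterion about willingness. Figure 1 note e equates visit 11 with visit 1 of the follow-up portion. The reason given in 3.3, separating the drug's effect from that of preventives, loses its force at visit 11, when the diary and the efficacy questionnaires end. Appendix C counts "noncompliance to investigational medicinal product administration; and use of prohibited medications" among possible important deviations and says "the sponsor will determine whether to discontinue the patient from the study or permit the patient to continue in the study", so withdrawal is not inevitable in practice.

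Most of this stands as evidence of intent: the ban was probably meant to end at EOT. It does not remove the conflict. The 4.1 lead-in decides who must meet criterion f, not for how long. Neither note e nor the completer rule limits 3.3, 5.5, Appendix H or 4.3. The discretion in Appendix C is not carried into the mandatory wording of 4.3. Sites should not have to infer the end of a rule that says patients must be withdrawn.

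A reader might go further and infer that late safety or ADA data will be lost, or that patient disposition becomes uncountable. The documents do not support either. Visit 12 is still requested after withdrawal, and Appendix B supplies a definition of completion at visit 11.

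**Conclusion.** The point holds as a minor inconsistency of wording. Read literally, a treated patient who takes verapamil between EOT and visit 12 must be withdrawn for care that 3.1 and Table 4 footnote k direct. This includes a CCH patient moved to follow-up after stopping the study drug. What it touches is patient care and the completeness of late safety and ADA follow-up. SAP section 7 plans no inferential analysis, so no test or estimate depends on it.

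The conclusion rests on two readings: that the study in 4.1 f and 3.3 includes follow-up, as 3.1, 5.5 and 7.1.2 indicate, and that standard of care includes at least verapamil, as 1.1.2 indicates.

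The 41% is a share of the calendar. It should not be read as a share of patients or of data, because the documents give no rate of preventive use after dosing and no case of a patient withdrawn for it. Nor do they support saying that the ban was meant to run to week 68.

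**What to change.** In 4.1 f and its Synopsis copy, 3.3, 5.5 and Appendix H, state that the ban, after the 1-month taper, applies to the double-blind treatment period and ends at the EOT/early withdrawal visit. Appendix H already bounds the steroid ban by the treatment period. Section 5.5 has to be included because 7.10 points to it. Limit 4.3 item 4 to the same period. Add a sentence to 4.3 saying that later preventive use is recorded as concomitant medication and does not end participation or visit 12 collection.

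The change should stop there. Patients still attending treatment-period visits would stay under the ban until EOT even if they are no longer dosed. They are still giving diary data, and lifting the ban earlier would cut against the purpose stated in 3.3.

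The cost is wording in six places (4.1 f, Synopsis, 3.3, 5.5, Appendix H, 4.3 item 4) and one added sentence. There are no new visits, tests or patients. Table 4 already asks about concomitant medication at visit 12, and SAP 8.12, using the categories in SAP 5.5, already summarises Appendix H preventives taken after the first dose.

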4.2. Patient Exclusion Criteria

Patients will be excluded from participating in the treatment portion of this study if they meet any of the following criteria:

- a. The patient has a history of any suicide attempt in the past or current active suicidal ideation, as measured by the eC-SSRS.
- b. Any finding in the 12-lead ECG performed as part of the EOT visit (visit 5) procedures for the pivotal studies considered clinically significant in the judgment of the investigator.
- c. Any finding that, in the judgment of the investigator, is a clinically significant abnormality, including serum chemistry, hematology, coagulation, and urinalysis test values (abnormal tests may be repeated for confirmation).
- d. Hepatic enzymes (ALT and AST) $>1.5 \times$ the upper limit of the normal range (ULN) after confirmation in a repeat test or suspected hepatocellular damage that fulfills criteria for Hy's law.
- e. Serum creatinine $>1.5 \times$ the ULN or evidence of clinically significant renal disease in the judgment of the investigator.

Patients rolling over only for safety follow-up and ADA who are not receiving study medication are not required to fulfil all inclusion exclusion criteria.

4.3. Withdrawal Criteria and Procedures for the Patient

Each patient is free to withdraw from this study at any time, without prejudice to their continued care. Patients must be withdrawn from this study if any of the following events occur:

1. Patient withdraws consent or requests discontinuation from this study for any reason.
2. Patient develops an illness that would interfere with his/her continued participation.

3. Patient is noncompliant with the study procedures and assessments or administration of IMPs (including noncompliance with wearable sensor substudy, if applicable) in the opinion of the investigator.
4. Patient takes prohibited concomitant medications as defined in this protocol.
5. A female patient has a confirmation of pregnancy during the study from a positive pregnancy test result.
6. The sponsor requests withdrawal of the patient.
7. Patient experiences an adverse event or other medical condition which indicates to the investigator that continued participation is not in the best interest of the patient.
8. The investigator and/or sponsor may withdraw an individual patient from the study at any time for any reason (eg, lack of efficacy, protocol deviation as defined in Section 10, noncompliance, or adverse event). In addition, patients with positive eC-SSRS findings or abnormal hepatic laboratory values (eg, ALT, AST, ALP, GGT, bilirubin [total, direct, or indirect], or INR) may meet criteria for discontinuation from the IMP as summarized in [Appendix J](#).

In the event that a patient was incorrectly enrolled and has already started taking the study drug, a risk/benefit evaluation should take place between the investigator and sponsor, and a strong clinical justification must be provided if the patient is not withdrawn from study drug.

Patients should be treated with standard of care after withdrawal from or termination of the study as appropriate.

Investigators should attempt to obtain information on patients in the case of withdrawal or discontinuation. Results of any evaluations and observations, together with a narrative describing the reason(s) for withdrawal, must be recorded in the source documents. The case report form (CRF) must document the primary reason for withdrawal or discontinuation.

See [Appendix F](#) for information regarding how the study will define and address lost to follow-up patients to help limit the amount and impact of missing data.

If a patient is withdrawn from the study for multiple reasons that include also adverse events, the termination page of the CRF should indicate that the withdrawal was related to an adverse event. An exception to this requirement will be the occurrence of an adverse event that in the opinion of the investigator is not severe enough to warrant discontinuation but that requires the use of a prohibited medication, thereby requiring discontinuation of the patient. In such a case, the reason for discontinuation would be “need to take a prohibited medication” and not the adverse event.

Should a patient decide to withdraw after administration of the IMP or should the investigator decide to withdraw the patient, all efforts will be made to complete and report all observations up to the time of withdrawal. A complete final evaluation at the time of the patient’s withdrawal should be made and an explanation given as to why the patient is withdrawing or being withdrawn from the study.

The reason for and date of withdrawal from the study must be recorded on the source documentation and transcribed to the CRF. If a patient withdraws consent, every attempt will be made to determine the reason.

All protocol-specified procedures/assessments should be performed at the early withdrawal visit (see [Table 4](#)). Patients who withdraw from the study will not be replaced.

A patient should only be designated as lost to follow-up if the investigational center is unable to establish contact with the patient after 3 documented attempts via 2 different methods (phone, text, e-mail, certified letter, etc). In the case of patients lost to follow-up, attempts to contact the patient must be made and documented in the patient's medical records and transcribed to the CRF.

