The pharmacokinetics (non-compartmental analysis; Study TV48125-PK-10078) of fremanezumab demonstrated an increase in C_{\max} and AUC values slightly greater than the dose proportionality over the sc dose range of 225 to 900 mg. Median time to maximum observed concentration (t_{\max}) values was generally 5 to 7 days post sc doses. Mean values for apparent total volume of distribution during the terminal phase (V_z/F) after a single sc dose ranged from 5.7 to 6.4 L at 225-mg to 900-mg sc doses. The mean apparent total plasma clearance (CL/F) ranged from 0.0777 to 0.0895 mL/min at this dose range. The mean $t_{1/2}$ ranged from 32.2 to 36.2 days. Fremanezumab exposure parameters and overall pharmacokinetic profile were similar for healthy Japanese and Caucasian subjects.

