7.1.8. Protocol Deviations Because of an Adverse Event

If a patient experiences an adverse event or medical emergency, deviations from the protocol may be warranted to ensure patient safety. After the event has stabilized or treatment has been administered (or both), the investigator or other physician in attendance must contact the physician identified in the Clinical Study Personnel Contact Information section of this protocol as soon as possible to discuss the situation. The investigator, in consultation with the sponsor, will decide whether the patient should continue to participate in the study. The same reporting process as for all other protocol deviations will apply. A noncompliant patient may continue taking the study treatment only if this does not jeopardize the patient's safety. The sponsor will assess each protocol deviation and decide whether any of these noncompliances should be reported to the Regulatory Authority as a serious breach of Good Clinical Practice (GCP) and the protocol.

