- Complete the PPSI and the PGIC scale.
- Collect the electronic diary device.
- Each patient's partner/family member completes the Impact on Partner and Family questionnaire. Partners/family members will be asked to attend the study visit with the patient or to return to the investigational center within ± 3 days of the patient's visit if unable to appear at the same time.
- Perform wearable sensor device check and compliance check for patients enrolled in the wearable sensor substudy.
- Collect wearable sensor device from patients enrolled in the wearable sensor substudy.

3. Procedures after IMP Treatment

Follow-up Visit (Visit 12 [Week 68 \pm 1 Week])

Patients who participate in the study in compliance with the protocol for the entire treatment period (ie, from visit 1 through visit 11) will be considered to have completed the study. Patients may be treated with standard of care following completion of visit 11. See Section 3.1 for the definition of the end of study.

Patients who complete the double-blind treatment period will have a follow-up visit approximately 7.5 months (5 half-lives) after the final dose of IMP. The following procedures/assessments will be performed at this visit:

- Perform vital signs measurements (includes systolic and diastolic blood pressure, pulse, and body temperature).
- Perform physical examination (including weight).
- Inquire about adverse events.
- Inquire about concomitant medications.
- Complete the eC-SSRS Since Last Visit version.
- Obtain a 5-mL blood sample for ADA analysis.
- Obtain a 5-mL urine sample for biomarker analysis.
- Obtain a 17-mL blood sample (8.5 mL for serum, 6 mL for plasma, and 2.5 mL for RNA) for biomarker analysis.

Patients who discontinue treatment prematurely must be encouraged to continue to attend the regular scheduled visits, and complete the prescribed safety and efficacy evaluations through the EOT visit (visit 11 [week 36]) and the follow-up visit (visit 12 [week 40]), if at all possible.

Patients who both discontinue treatment and also withdraw from the study should have EOT (early withdrawal) visit procedures/assessments (see [Table 4](#)) performed on the last day the patient receives the IMP, or as soon as possible thereafter. The patient should also return for the follow-up visit approximately 7.5 months after the last dose of IMP if at all possible.

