b Patients will return for unscheduled visits in the event of any safety concern.

ADA=antidrug antibody; EOT=end-of-treatment; IMP=investigational medicinal product.

^{&#}x27;Last Assessment' may be derived for analysis purpose and is defined as the last observed postbaseline data. For patients who withdraw from the study, their data at the early withdrawal visit will be excluded from the by-visit sections but will be included in the Last Assessment section.

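### Protocol Section 4.3 item 4 forces study withdrawal for prohibited-medication use and so ends the interim safety visits, while Appendix C and Section 7.1.8 allow continuation and no precedence is stated

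*Protocol*

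**What the plan says.** Section 4.3 of the protocol opens with a list of events for which withdrawal from the study is mandatory. Item 4 is "Patient takes prohibited concomitant medications as defined in this protocol", with no exception attached. A later paragraph of the same section covers an adverse event that is not serious enough in itself to stop the patient but "requires the use of a prohibited medication, thereby requiring discontinuation of the patient". In that case the CRF records the medication, not the adverse event, as the reason.

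The prohibited drugs are in Appendix H: five cluster headache preventives, to be tapered within 1 month of entry, and steroids ("Systemic steroids are not allowed during the double-blind treatment period of this long-term extension study").

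Appendix C names use of prohibited medications as a possible important deviation and then says that "the sponsor will determine whether to discontinue the patient from the study or permit the patient to continue in the study", with the medical expert's documented approval. For deviations arising from an adverse event or emergency, Section 7.1.8 says: "The investigator, in consultation with the sponsor, will decide whether the patient should continue to participate in the study".

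Appendix B separates two paths. For those who only stop study drug, "Patients who discontinue treatment prematurely must be encouraged to continue to attend the regular scheduled visits". Those who also leave the study have the early-withdrawal assessments and are then asked back about 7.5 months after the last dose.

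SAP Section 4.4 says of patients who withdraw that "their data at the early withdrawal visit will be excluded from the by-visit sections but will be included in the Last Assessment section".

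**The concern.** There are two problems. First, a site facing one and the same event can read a compulsory withdrawal in Section 4.3 and a discretionary continuation in Appendix C or Section 7.1.8.

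Second, settling the matter in favour of Section 4.3 does not remove the difficulty, because item 4 puts the patient on the Appendix B path that has no interim visits. The documents describe two routes to that outcome: restarting a preventive that the protocol made the patient taper, and an adverse event that needs a disallowed drug. Both can be related to how the patient is doing, so the missing laboratory, ECG, vital-sign and weight data need not be missing for unrelated reasons. In the second route the coded withdrawal reason will not show that an adverse event lay behind it.

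The stated purpose of banning preventives (Section 3.3) is to separate drug effects from theirs. That argues for stopping study drug and marking the data. It does not argue for ending observation.

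**Working it through.** **Which rule governs**

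- Section 4.3 item 4: compulsory, and from the study, not only from study drug.
- Section 4.3, later paragraph: discontinuation is again required, even if the adverse event alone would not justify it.
- Section 4.3 item 8: the investigator or sponsor may withdraw a patient for a protocol deviation. This is a discretionary rule in the same list.
- Appendix C: names the same event and leaves the outcome to the sponsor.
- Section 7.1.8: limited to adverse events and emergencies, but there it directly meets the later paragraph of Section 4.3.
- Amendment 03 summary (change log): says that restarting a preventive means leaving the study, and also classes such cases as important deviations. It does not mention steroids, and its classification leads back to Appendix C.

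None of these places states precedence.

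**What item 4 removes**

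Inputs, from Table 4 of the protocol and SAP Sections 8.8 to 8.11, restricted to visits 2 to 11 because visit 12 is requested either way:

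- laboratory tests and ECG: visits 4, 7, 10, 11
- vital signs: visits 2 to 11
- physical examination with weight: visits 2, 4, 5, 7, 8, 10, 11

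Net loss = occasions still scheduled through visit 11, minus 1 for the early-withdrawal set.

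| Withdrawal just after | Laboratory/ECG | Vital signs | Examination and weight |
|---|---|---|---|
| Visit 1 | 4 − 1 = 3 | 10 − 1 = 9 | 7 − 1 = 6 |
| Visit 4 | 3 − 1 = 2 | 7 − 1 = 6 | 5 − 1 = 4 |
| Visit 7 | 2 − 1 = 1 | 4 − 1 = 3 | 3 − 1 = 2 |
| Visit 10 | 1 − 1 = 0 | 1 − 1 = 0 | 1 − 1 = 0 |

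Preventives may be tapered for up to 1 month, so a restart would ordinarily arise at about visit 2 (week 4) or later. Just after visit 2 the net losses are 4 − 1 = 3, 9 − 1 = 8 and 6 − 1 = 5. The visit 1 row therefore applies mainly to systemic steroids.

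In the by-visit summaries the early-withdrawal set does not count (SAP Section 4.4), so the loss there is the number before the subtraction: 4 / 3 / 2 / 1 for laboratory and ECG variables, 10 / 7 / 4 / 1 for vital signs, and 7 / 5 / 3 / 1 for weight. The set is still used in Last Assessment, in the potentially clinically significant value summaries and in the ECG worst-value shift.

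**Length of the gap**

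Table 4 puts the last dose at week 36 and visit 12 at week 68, and 68 − 36 = 32 weeks. For a last dose at week 0 / 12 / 24 / 36, the follow-up falls at about week 32 / 44 / 56 / 68. Section 3.1 gives this interval as 7.5 weeks for patients who withdraw. The synopsis, Table 4 and Appendix B give 7.5 months, which I take as intended.

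**Is the early part of the gap drug-free?**

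Section 1.2.2.1 says that the mean half-life "ranged from 32.2 to 36.2 days". With simple first-order decline from the last active dose, fraction remaining = 2^(−days / half-life):

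- 28 days: 0.547 to 0.585
- 56 days: 0.300 to 0.342
- 84 days: 0.164 to 0.200

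The half-life comes from single subcutaneous doses in healthy subjects, so these fractions are indicative only. They suffice to show that the first missed visits fall while drug is still present.

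**The case against.** **Safety follow-up continues.** A reader might infer that a withdrawn patient drops from four-weekly visits to no safety follow-up, or that adverse events and suicidality data are lost. The documents do not support that. Section 7.1.2 has adverse events recorded through the follow-up visit, and both it and Appendix B require ongoing events to be monitored. SAP Section 8.3 sets no end date for treatment-emergent events. The eC-SSRS at visit 12 asks about the period since the last visit, so it spans the gap, although with longer recall. This objection stands in full, and I do not count eC-SSRS assessments as lost.

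**The protocol accepts sparse follow-up elsewhere.** About 240 safety-only patients follow Table 5, and chronic cluster headache patients told to stop study drug are directed to that portion. This is true. But Table 5 has no interim visits and no laboratory, ECG or vital-sign assessments, whereas Appendix B asks more of treated patients who stop early. Prohibited-medication users are closer to the latter.

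**The texts can coexist.** Section 4.3 is specific and Appendix C is general, and the Amendment 03 summary applies both. That shows the sponsor's probable intention for restarted preventives. It is not operative text and leaves steroids open.

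**Continued visits mix in other drugs' effects.** Off-drug visits on verapamil or lithium would enter by-visit tables by treatment group. This stands, and the fix has to deal with it.

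**Little is left to change.** SAP Section 2.1 gives completion in Q2/2019. SAP Sections 5.2 and 5.8 already summarise withdrawals by reason and important deviations by category. This stands too, and it limits what can still be gained.

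**Conclusion.** The point holds, at moderate weight. Section 4.3 and Appendix C give different outcomes for the same event, Section 7.1.8 does so in a narrower set of cases, and nothing ranks them. Taken literally, item 4 removes up to 3 laboratory/ECG sets, 9 vital-sign assessments and 6 examinations with weight per patient. The loss falls to none for withdrawal after visit 10. It is confined to those scheduled measurements.

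The counts assume that the early-withdrawal assessments are done and that the patient would otherwise have attended every visit. The total effect cannot be sized, because the documents do not say how many patients took a prohibited drug. The study is descriptive, so no test or power is affected. What suffers is the completeness of the long-term safety record in a subgroup whose departure may be related to their condition.

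**What to change.** - Reword item 4 and the later paragraph of Section 4.3 to require discontinuation of study drug. With consent, the patient continues at the scheduled safety visits through visit 11 (week 40) and at visit 12 (week 68, or about 7.5 months after the last dose), using the existing Appendix B path.
- Correct that path's labels: Appendix B gives visits 11 and 12 as weeks 36 and 40, while Table 4 gives weeks 40 and 68.
- State that this rule governs over Appendix C and Section 7.1.8 for prohibited medications.
- Flag all data after the event (diary, laboratory, ECG, vital signs) as off study drug and on prohibited medication, so that by-visit tables can be shown with and without them.

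The cost is protocol wording, a note to sites, a few more off-treatment visits and one extra flag. No new procedure is needed.

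If visits are already finished, add one item to the planned disposition-by-reason summary (SAP Section 5.2): the last scheduled visit attended by each patient withdrawn for this reason.
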